1. PURPOSE OF THE STUDY AND BACKGROUND

1.1. Purpose of the study

The purpose of this study is to compare the efficacy of a bioabsorbable steroid eluting implant (Propel mini stent or Propel contour stent) vs a steroid impregnated nasal dressing (triamcinolone in Nasopore) for surgical outcomes after endoscopic frontal sinus surgery in patients with chronic rhinosinusitis with nasal polypsis.

1.1. Background

Chronic rhinosinusitis (CRS) is defined by persistent sinonasal symptoms (nasal obstruction, facial pressure, nasal discharge, hyposmia) lasting at least 12 weeks and by objective findings of paranasal sinus inflammation.¹ CRS with nasal polypsis (CRSwNP) represents a subset of CRS defined by the above criteria along with the presence of nasal polyps in the middle meatus and has a variety of underlying causes.² Overall, cases CRSwNP respond well to endoscopic sinus surgery (ESS) with improvement in quality of life, symptom scores and endoscopic appearance.³ However, surgical treatment of the frontal sinus has been shown to be more challenging with higher rates of recurrent sinus disease. Factors associated with failure of frontal sinus ESS include advanced disease at presentation, prior ESS, inflammation or scarring in the frontal recess, middle turbinate lateralization, size of frontal sinusotomy and retained/residual frontal recess cells.^{4,5,6} Given these findings, meticulous surgical planning and removal of all obstructing bony partitions and diseased mucosa within the frontal sinus is advocated.

Additionally, in an attempt to decrease frontal sinus ESS failure, many methods of improving post-operative healing such as nasal saline and/or corticosteroid irrigations, oral corticosteroids, sinus stents, and more recently steroid releasing or impregnated stents/dressings have been used.^{2,7-10} Of these approaches, there are only 2 Food and Drug Administration approved steroid releasing sinus implants used at the frontal sinus opening (FSO).¹¹ It has been shown in a randomized controlled trial that steroid releasing sinus implants can improve both subjective and objective outcomes after endoscopic frontal sinus surgery compared to controls.¹¹ However, to date there has been no comparison of steroid releasing frontal sinus implants vs. other means of direct steroid delivery to the FSO after ESS, such as via a steroid impregnated dressing. Presently both stents and dressings are used routinely after ESS, but typically any one patient would get one or the other treatment for each of their sinuses.

The present study was designed to evaluate and compare the surgical outcomes of frontal sinusotomy and placement of a steroid releasing implant vs. a steroid impregnated nasal dressing within the FSO with the subject serving as their own control by receiving the stent and dressing randomly assigned to either the left or right sinus.

2. STUDY DESIGN

2.1. Overview

This is a single center, randomized & controlled trial comparing the efficacy of the Propel mini or contour stent vs. Nasopore impregnated with triamcinolone acetonide at reducing frontal sinus opening stenosis and polypoid edema after ESS in patients with CRS with polyposis. Eligible subjects who undergo standard of care bilateral frontal sinusotomy will have each frontal sinus randomly assigned to either a Propel steroid eluting stent or a Nasopore nasal dressing impregnated with 2.5 ml of triamcinolone acetonide 40 mg/ml. The specific Propel stent will be chosen based on the shape of frontal sinus opening and best fit as decided by the operating surgeon. Patients will be reassessed on approximately post-operative day 7, 14, 30, 90 days, 6 months, and 12 months at their SOC follow-up visits. On the day 14 visit, the frontal sinus Propel stent and Nasopore will be completely removed per SOC. Video will be taken of the frontal sinus opening, and assessed for scarring/adhesions, presence of polypoid edema, frontal sinus patency, need for oral steroids or other interventions. Additionally, endoscopic scoring of frontal sinus by the above measures will be evaluated by 2 independent sinus surgeon reviewers. The reviewers will also be asked to rank the two frontal sinus openings as better, same or worse, compared to the opposite side.

2.2. Rationale for Study Design

Steroid impregnated bioabsorbable implants can reduce scarring and inflammation post-operatively in the ethmoid cavity. Recent studies have also shown that an FDA approved bioabsorbable steroid releasing implant placed in the frontal sinus after endoscopic sinus surgery can improve surgical outcomes. However, no study to date has compared different methods of steroid delivery to the frontal sinus after endoscopic sinus surgery. Our study will add to the limited data in the literature regarding the efficacy of steroid eluting implants placed in the frontal sinus opening after endoscopic sinus surgery and provide a direct comparison of two established steroid delivery methods. Patients will serve as their own control in order to provide a direct comparison between both steroid delivery systems while limiting bias from interpatient variability.

3. CHARACTERISTICS OF THE RESEARCH POPULATION

3.1. Subject Characteristics

- a) **Number of Subjects:** We plan to enroll 30 total subjects (60 frontal sinusotomies total): each patient will have undergone bilateral frontal sinusotomy
- b) **Gender and Age of Subjects:** Subjects 18 years of age and older will be included in the study. There will be no gender restrictions.
- c) **Racial and Ethnic Origin:** There will be no restriction based on race or ethnicity.

3.2. Inclusion and Exclusion Criteria

1) Inclusion Criteria:

- a) Adults aged 18 and older
- b) Diagnosis of chronic rhinosinusitis with nasal polyps based on the American Academy of Otolaryngology–Head and Neck Surgery guidelines
- c) Patient scheduled for bilateral endoscopic sinus surgery with evidence of bilateral frontal sinus disease based on Computed Tomography (Lund-Mackay score greater than or equal to 1).
- d) At the time of surgery bilateral frontal sinusotomy of type Draf 2a or 2b was performed using the same technique on both sides.
- e) Bilateral endoscopic sinus surgery performed successfully without complication
- f) Frontal sinus opening diameter greater than 4.0 mm achieved (4 mm olive tipped suction easily passed into frontal sinus)

2) Exclusion Criteria:

- a) Any patient who had frontal sinus surgery for tumor
- b) Allergy to mometasone and/or triamcinolone
- c) Frontal sinusotomy type Draf 1 or Draf 3 performed
- d) One or both frontal sinus openings not amenable to implant placement
- e) Patients with chronic oral steroid dependent conditions
- f) Invasive fungal sinusitis
- g) Immune deficiency

Pregnancy precludes elective endoscopic sinus surgery due to the risks of general anesthesia. Consequently pregnant women will not be included in this study.

3.3. Discussion of Subject Population

Patients enrolled in the study have been diagnosed with chronic rhinosinusitis with nasal polyps and deemed appropriate for surgical intervention. A complete pre-surgical work up and discussion regarding the treatment options including observation, continued medical treatment and surgical intervention will be offered as is standard for any patient with this condition. After discussion of the risks and benefits of surgery vs medical therapeutic options some patients will choose surgery and they will be offered participation in the study.

The ESS surgical procedure typically has a 1% complication rate and approximately 5% frontal sinusotomy failure rate at the time of surgery (inclusion criteria e-f). Thus by ensuring subjects meet inclusion criteria a) through d) and that none of the exclusion criteria apply prior to enrollment, we would have a very low rate of screen failure, where an enrolled subject does not ultimately meet inclusion criteria e) and f).

4. SUBJECT IDENTIFICATION, RECRUITMENT AND CONSENT

4.1. Method of Subject Identification and Recruitment

Patients will be recruited from the clinical practice of the principal investigator. Preferentially subjects will be approached by an ENT resident (listed as study personnel) for consent to mitigate the potential coercion of having their surgeon inquire on their willingness to participate. However logistics may dictate that the PI or SC are the only people available and they may also obtain consent.

4.2. **Process of Consent**

If eligible, patients will be approached by an approved study team member to discuss the study prior to their surgery date, typically in person after they have chosen to proceed with sinus surgery. In a private room, candidate subjects will be assured that their decision to participate or not to participate will not affect the medical care that they can expect. If they are interested in participation, they may take the consent form home or they may provide consent at that time. When ready to consent, the teach-back method will be used to ensure that the subject understands their participation in the study.

The person obtaining consent will pass the form to the SC. Consent will be documented by the SC in a consent log in REDCap and signed forms will be stored in the Otolaryngology Department Research Office.

5. METHODS AND STUDY PROCEDURES

Screening may take place at the initial presentation to the principal investigator or a pre-operative visit up to 90 days prior to a planned Operative procedure. As part of their standard of care pre-surgical work-up subjects will provide a complete medical and sinonasal history and a complete head and neck exam including bilateral rigid nasal endoscopy will be performed. Pictures from this standard endoscopy will be taken of the frontal recess or frontal sinus opening if possible. Patients will also have had a CT sinus scan performed pre-operatively for surgical planning and intra-operative image guidance. Subjects will consent to this medical information being released to the study, which will be abstracted when the subject completes the study. If any patients do not have evidence of bilateral frontal sinus disease based on CT results (Lund-Mackay ≥ 1), they will be screen-failed prior to surgery and will not be randomized.

Pre-operatively patients may receive oral steroids and/or antibiotics as deemed medically necessary. Each patient will receive the indicated sinus surgery based on their exam and symptoms, and in no way will be influenced by their decision to decline or enroll in the study. For treatment, the patients will undergo bilateral endoscopic sinus surgery which will include bilateral frontal sinusotomy of Draf 2a or 2b type as previously described in the literature. At the conclusion of the procedure, if the patient still meets all inclusion criteria, one frontal sinus will be randomly assigned using the envelop method to receive a bioabsorbable steroid releasing implant and the other frontal sinus will receive a bioabsorbable nasal dressing impregnated with steroid. Patients will taper their pre-operative oral steroids from 40 mg daily to 10 mg daily and continue use until their first post-operative visit and then stop. Post-operative antibiotics will be prescribed as deemed medically necessary. Patients will be encouraged to irrigate their sinus twice daily with a high volume (240 ml bottle) of normal saline solution. Patients will be allowed to continue nasal steroid sprays and/or orally inhaled sprays for control of asthma. The patient

will have standard post-operative visits at approximately 1 week, 2 weeks, 30 days, 90 days, 6 months and 12 months. On post-operative day 14 the first endoscopic evaluation of the frontal sinus opening after implant removal will be performed. Video is routinely recorded and this will be copied for the study, edited to remove any identifying features of the subjects, for review and scoring by qualified independent reviewers. If at any of the post-operative visits oral steroids, antibiotics or in-office procedures is deemed medically necessary this will be allowed and recorded as part of the study results. Subjects' participation will conclude at the 12 month visit.

Schedule of Activities (R Research/SOC Standard of Care)

Visit	0 (Screening)	Operative Visit	FUV 1	FUV 2	FUV 3	FUV 4	FUV 5	FUV 6
Visit timing	Up to 90 days pre-operative	Day 0	1 week post op (+/-3 days)	2 weeks (+/-5 days)	1 month (28 to 56 days post op)	3 months (+/-14 days)	6 months (+/-21 days)	12 months (+/-21 days)
Obtain informed consent/confirm eligibility (R)	X							
Medical and sinonasal history evaluated (SOC)	X							
Bilateral endoscopic sinus surgery (SOC)		X						
Confirm eligibility/ Randomize treatment (R)		X						
Placement of frontal sinus opening treatments (SOC)		X						
Obtain validated SOC sinonasal symptom and quality of life questionnaires (SOC)	X		X	X	X	X	X	X
Complete ENT and sinonasal exam including rigid endoscopy (SOC)	X		X	X	X	X	X	X
Rigid endoscopy with documentation (SOC)	X	X	X	X	X	X	X	X
Abstraction from endoscopy record on frontal sinus opening scarring, polypoid edema,				X	X	X	X	X

overall condition for data analysis and external review (R)								
Adverse event review (R)			X	X	X	X	X	X

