5.1. Efficacy Assessments

Efficacy will be determined by comparing the right and left frontal sinus opening after removal of the stent and dressing on POD 14, and then around day 30, 90, 6 month and 12 months. The frontal sinus opening will be assessed with a rigid endoscope, using 30, 45 and/or 70 degree scopes as necessary. Our primary efficacy outcome will be a grade assigned by 2 blinded, independent sinus surgeon experts as: better, worse or same, comparing overall appearance of the study subject's frontal sinus openings after implant removal.

Additionally, the frontal sinus opening will also be graded on an adhesion/scarring scale, a polypoid edema scale, size in mm of the opening as measured by a visual analog scale/comparison to 4 mm suction, and visualization of the roof of the frontal sinus.

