7.4. Subject Enrollment/Randomization

Subjects will be enrolled on the basis of the inclusion and exclusion criteria and signed informed consent. Subjects will be randomized using the envelope method to have either the Bioabsorbable steroid releasing stent placed or Nasopore soaked with 2.5 ml of triamcinolone acetonide 40 mg/ml placed in the left frontal sinus opening. The right frontal sinus opening will

have the other device placed. Patients will serve as their own comparison group and as such there will be a 1:1 ratio of frontal sinus openings treated with each method.

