11.2. Sample Size Determination

Sample size is based on a non-inferiority design. Based on historical data it can be estimated that frontal sinusotomy will have a patency (success) rate of 85%. Given the lack of any known evidence to the contrary, we will assume that both the Propel mini/contour stent and the Nasopore impregnated with 2.5 mls of Kenalog 40 mg/ml placed in the FSO after ESS will result in a patency rate of 85%. Given that all prior clinical trials investigating local delivery of steroid to the FSO have utilized the Propel mini or contour stent, this will serve as our “standard therapy” group. Using an $\alpha= 0.05$, Power= 80%, and a minimum significant difference (δ) of 25%, 28 patients (56 total frontal sinus interventions) will be enrolled to be 80% sure that the upper limit of a one-sided 95% confidence interval will exclude a difference in favor of the “standard therapy” group of more than 25%. The ESS surgical procedure typically has a 1% complication rate and frontal sinusotomy failure rate of approximately 5%. Thus by ensuring subjects meet inclusion criteria a) through d) and that none of the exclusion criteria apply prior to enrollment, we would have a very low rate of screen failure, where an enrolled subject does not ultimately meet inclusion criteria e) and f). Hence enrolling 30 subjects should be sufficient to reach our statistical needs.

[figure not shown]
11.3. Planned Statistical Analysis:

Primary outcome measure: Grading by a blinded independent sinus expert as to whether the the propel sinus stent frontal sinusotomy side is better, worse or the same.

[figure not shown]
Secondary outcome measures:

1. Mucosal/polypoid edema
2. Adhesion/scarring
3. Size of frontal sinus opening
4. Visualization of the frontal sinus roof
5. Need for post-operative oral steroids
6. Need for post-operative interventions beyond normal debridement

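### The opening made at surgery is documented on Day 0 but not abstracted, so the secondary opening-size outcome has no baseline and gives up precision

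*Combined protocol and SAP*

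**What the plan says.** - **Aim (section 2.1).** The two treatments are compared for efficacy "at reducing frontal sinus opening stenosis and polypoid edema after ESS in patients with CRS with polyposis".
- **Schedule (section 5).** The row "Rigid endoscopy with documentation (SOC" is marked at screening, at the Operative Visit and at FUV 1 to 6. The research row "Abstraction from endoscopy record on frontal sinus opening scarring, polypoid edema" (continuing to overall condition, for data analysis and external review) is marked at FUV 2 to 6 only.
- **Size outcome (sections 5.1 and 11.3).** Section 5.1 compares right with left from post-operative day 14 on and defines "size in mm of the opening as measured by a visual analog scale/comparison to 4 mm suction". Section 11.3 lists opening size third among six secondary outcomes, and its readable text gives no baseline, change definition or analysis method.
- **Day 0 size (section 3.2).** The only use made of it is an eligibility threshold: each opening must exceed 4.0 mm, shown by passing a 4 mm suction.
- **Order of events (sections 3.2, 5 and 7.4).** The same sinusotomy technique is used on both sides, eligibility is confirmed at the end of surgery, and side is then assigned: "Subjects will be randomized using the envelope method".

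**The concern.** Stenosis is a loss of size, so measuring it directly needs a starting size. As the outcome stands, a side opened to 9 mm that narrows to 5 mm would score the same as a side that began and stayed at 5 mm (invented figures, for illustration). Using the same technique on both sides, with both above 4 mm, does not make the two openings equal.

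Any left-right difference present at the end of surgery carries into the follow-up comparison as noise. With about 28 pairs, chance can also leave one treatment with the larger openings on average. A per-side Day 0 value would deal with both. It can be observed only once, because the devices are then placed and healing begins.

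**Working it through.** **1. The plan's own figure.** Section 11.2 gives "Power= 80%, and a minimum significant difference (δ) of 25%, 28 patients (56 total frontal sinus interventions) will be enrolled", with the criterion that the "upper limit of a one-sided 95% confidence interval will exclude a difference in favor of the “standard therapy” group of more than 25" percent, and assumes both treatments "will result in a patency rate of 85" percent. The usual unpaired non-inferiority formula is

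n = 2p(1−p)(z₀.₉₅ + z₀.₈₀)² / δ² = 2 × 0.85 × 0.15 × (1.645 + 0.842)² / 0.25² = 25.2, so 26 per treatment.

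That is within two of the stated 28. The calculation concerns binary patency and does not involve opening size, so nothing below changes it.

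**2. Is raw size biased?** Let D₀ be the stent-minus-dressing size difference at Day 0 and D₁ the same difference at follow-up. Side is assigned at random after both openings exist, so E(D₀) = 0 and E(D₁) = E(D₁ − D₀). In a simulation of 28 pairs with a true effect of 0.50, raw size and change from Day 0 both averaged 0.50. There is no bias.

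**3. Precision with one covariate.** Let r be the correlation of D₀ with D₁. Regressing D₁ on D₀ and estimating the effect at D₀ = 0 multiplies the variance by

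(1 − r²) × [1 + 1/(n − 3)] = (1 − r²) × 1.04 at n = 28.

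The bracket is the cost of estimating the slope. A 20,000-run simulation gave the same values. Equivalent pairs are 28 divided by the factor. The detectable difference (two-sided 0.05, 80% power) is 0.55 SD of D₁ unadjusted, multiplied by the square root of the factor when adjusted.

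| Assumed r | Variance factor | Equivalent pairs | Detectable difference (SD of D₁) |
|---|---|---|---|
| 0 | 1.04 | 26.9 | 0.56 |
| 0.3 | 0.95 | 29.6 | 0.54 |
| 0.5 | 0.78 | 35.9 | 0.49 |
| 0.7 | 0.53 | 52.8 | 0.40 |

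**4. Chance imbalance.** The mean of D₀ over 28 pairs has standard error 1/√28 = 0.19 SD of D₀. An imbalance of one standard error shifts the raw comparison by r × 0.19, which is 0.06, 0.09 or 0.13 SD of D₁ at r = 0.3, 0.5 or 0.7.

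**5. Simple change score.** With equal SDs at the two times, its variance relative to raw size is 2(1 − r): 2.0, 1.4, 1.0 and 0.6 at r = 0, 0.3, 0.5 and 0.7. It is less precise than raw size whenever r is below 0.5.

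**6. Adding a term for the side that received the stent.** With two covariates the bracket becomes about 1 + 2/(n − 4) = 1.083. The factors are then about 1.08, 0.99, 0.81 and 0.55. Simulations put the value at r = 0 at 1.09 to 1.10. The gain at r = 0.3 all but disappears.

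The documents give no SD or correlation for opening size, so every r here is an assumption.

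**The case against.** Several stronger readings are tempting, and the documents do not support them.

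- *The trial measures the wrong thing, or is biased.* The primary outcome is a blinded ranking of overall appearance, the sample size rests on patency, and size is one of six secondary outcomes. Step 2 shows that raw size estimates the same expected difference as narrowing does.
- *The baseline is free because Day 0 is filmed.* The Operative Visit row says only that endoscopy is documented. The statement in section 5 that video is routine follows the day 14 evaluation, and section 9 describes footage brought from the clinic. Nothing says that the Day 0 record is video, shows both finished openings, precedes placement or includes the suction. The suction test is pass or fail, so a new measurement may be needed.
- *Side must be in the model.* An 18:10 or more uneven split has probability 0.185 only if the envelopes are unblocked, which the documents do not state either way. No effect of side is documented.
- *Pre-operative CT is wasted.* It determines eligibility, section 5 says pre-operative information will be abstracted, and it predates the opening in question.

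Two cautions also stand. Size is a visual estimate against a 4 mm suction, so a high r cannot be presumed. Figures next to 11.3 are not shown, so a baseline term there cannot be excluded. Even so, the schedule marks no Day 0 abstraction that would supply such a term.

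**Conclusion.** The point holds in limited form. A per-side post-surgical baseline for opening size is within reach and the plan does not collect it for analysis. The consequence is lost precision, exposure to chance left-right imbalance and no direct measure of narrowing, for one secondary outcome. It does not cause bias, and it leaves the primary ranking and the 28 (30 enrolled) subjects unaffected.

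The gain depends on an unknown correlation: about 5% of the variance at r = 0.3, 22% at 0.5 and 47% at 0.7, against a loss of about 4% at r = 0. It also depends on Day 0 size being gradable on the scale used at follow-up.

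**What to change.** 1. Mark the Operative Visit in the abstraction row. Record each side's opening size after sinusotomy and before device placement, preferably before the envelope is opened, on the same 4 mm suction reference. Take it from the Day 0 documentation if that shows the openings; otherwise note it when the suction is passed for eligibility.
2. State in 11.3 that size is analysed as the within-patient stent-minus-dressing difference, adjusted for the Day 0 side difference.
3. Report change from Day 0 descriptively only, as the direct picture of narrowing.
4. Leave the better/same/worse ranking unadjusted. Treat a term for side as optional, since it would raise the loss at r = 0 from about 4% to about 8–10%.

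The cost is one more abstraction per subject, a short measurement at surgery if the record does not show the openings, and about 4% of precision if the baseline proves uninformative. Treatment, visits and sample size do not change.
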